6.3.4. Instructions for Discontinuation of Study Drug Administration for Safety Concerns

If after appropriate consideration of ataluren interruption/modification and consultation with the PTC Therapeutics medical monitor, it is not appropriate for a subject to continue with study treatment, then ataluren should be permanently discontinued. After permanent discontinuation of ataluren for a safety concern, and if the initial event was reported as a SAE, then a follow-up SAE report form should be completed. In the case of a treatment discontinuation due to an event that is not an SAE, the PTC Therapeutics medical monitor should be notified (see Section 9). In addition, details regarding the reasons for discontinuation and the adverse events leading to the discontinuation should be recorded in the source documents and in the appropriate CRF. The End of Treatment Visit CRF should be completed and appropriate follow-up (at ~6 weeks as per protocol or until recovery from or stabilization of the adverse event, whichever comes last) should be instituted.

6.4. Concomitant and Supportive Therapy

Other than ataluren, any treatments (including prescription and non-prescription drugs, health foods, herbal remedies, self-prescribed drugs, street drug, tobacco products, or alcohol) that are

taken by a subject during the screening period, during ataluren administration, and for ≥6 weeks after discontinuation of ataluren are considered concomitant medications. Information regarding any concomitant medications will be recorded in the source documents and in the concomitant medication CRF.

6.4.1. Aminoglycosides or Other Potentially Nephrotoxic Agents

Renal abnormalities were observed in an international, multicenter, double-blind, placebo-controlled Phase 3 trial evaluating ataluren in patients ≥6 years of age with nonsense mutation cystic fibrosis in patients receiving concomitant ataluren and intravenous (IV) aminoglycosides (as described in the Ataluren Investigator Brochure). In patients who require treatment for serious infections, investigators should substitute other antibiotics for systemic aminoglycosides when clinically appropriate.

If IV aminoglycosides are administered, study drug must be interrupted during the course of these antibiotics. Study drug interruption should be considered with concomitant use of other potentially nephrotoxic antibiotics (eg, vancomycin). Caution should be exercised during concomitant use of other potentially nephrotoxic agents. Patients requiring IV aminoglycoside or other potentially nephrotoxic antibiotic should be closely monitored in an appropriate setting. In patients receiving potentially nephrotoxic antibiotics such as IV aminoglycosides or vancomycin, antibiotic drug levels and serum creatinine and BUN should be followed closely. The antibiotic trough level and creatinine and BUN should be measured within 24 to 48 hours of administration of the first antibiotic dose, and further antibiotic dosing should be based on these results. Trough levels should be measured at intervals during the course of antibiotic treatment. Creatinine and BUN should be measured prior to initiating IV aminoglycoside or vancomycin therapy and at least twice a week during the course of antibiotic treatment.

6.4.2. Hydration

Because of the potential risk of renal dysfunction during periods of dehydration in patients receiving ataluren, it is important to encourage study patients to maintain adequate hydration throughout the study. Patients should be adequately hydrated prior to receiving potentially nephrotoxic agents such as aminoglycosides or vancomycin, and hydration status should be carefully monitored throughout the administration of these agents. Investigators should be particularly vigilant with patients who are experiencing nausea, vomiting, diarrhea, or fever, or who have laboratory evidence of dehydration.

6.4.3. Cardiac Drugs for CHF Prophylaxis/Treatment

Cardiac drugs (eg, ACE inhibitors, ARBs, beta-blockers, etc) may be used in the treatment of congestive heart failure (CHF) in nonambulatory patients with DMD and may increasingly be considered for use as prophylaxis against symptomatic cardiac dysfunction in younger boys with the disease [Bosser 2004, American Academy of Pediatrics 2005, Duboc 2005, Kajimoto 2006, Ramaciotti 2006].

In patients who are receiving an ACE inhibitor or ARB, monitoring of plasma renin and aldosterone values in patients with treatment-emergent evidence of adrenal dysfunction should be conducted with the understanding that high renin values or low aldosterone values may not

represent definitive evidence of adrenal toxicity. In patients on these drugs who develop other evidence for primary adrenal insufficiency (eg, elevated plasma ACTH concentration), reassessment of plasma renin and aldosterone after interruption of ACE inhibitor or ARB treatment may be warranted.

Subjects who require initiation, interruption, dose modification, or reinstitution of CHF prophylaxis/treatment may continue ataluren dosing.

6.4.4. Drugs Metabolized by Cytochrome P450 Enzymes

As the primary route of ataluren metabolism is via glucuronidation by UGT1A9, clinically significant interactions between ataluren and co-administered drugs metabolized by cytochrome P450 enzymes (CYPs) are unlikely. In particular, ataluren is not an inhibitor of CYP1A2, CYP2B6, CYP2C19, CYP2D6, and CYP3A4/5, and does not have induction potential on the major CYP enzymes.

In vitro, ataluren is a weak inhibitor of CYP2C8 and CYP2C9, but in vivo drug-drug interactions mediated by these enzymes are not expected according to the criteria described in the EMA guideline on the investigation of drug interactions [EMA 2012]. As an added measure of safety, investigators should pay specific attention to use of drugs that are known substrates of these enzymes, particularly when such drugs may have a low therapeutic index. The study manual includes a list of clinically available drugs that are metabolized by CYP2C8 or CYP2C9 so that investigators may use appropriate judgment in deciding how to monitor patients who may be receiving such substrates.

Drugs that are metabolized by CYP2C8 or CYP2C9 that have low therapeutics indices (in particular, paclitaxel for CYP2C8 and coumarin anticoagulants [eg, warfarin], phenytoin, or tolbutamide for CYP2C9) may be of particular concern and patients who require the use of these drugs will not be enrolled to the study. Coumarin anticoagulants are cleared by CYP2C9 and increases in plasma concentrations of coumarin anticoagulants may result in serious clinical consequences. For patients who require anticoagulation during the study, use of an alternative form of anticoagulation (eg, fractionated heparin) should be considered. Phenytoin is metabolized by CYP2C9 and concomitant use with ataluren may be of potential concern. For patients who require anticonvulsant therapy during the study, use of alternative anticonvulsant drugs should be considered.

The metabolism of losartan to its active metabolite may, in part, be mediated by CYP2C9; thus, investigators should be aware that administration of ataluren may hypothetically change losartan effectiveness. However, concomitant use of losartan and inhibitors of CYP2C9 has not been examined.

6.4.5. Other Potential Drug Interactions

Based on in vitro studies, ataluren is a substrate of UGT1A9 and breast cancer resistant protein (BCRP). Caution should be exercised when ataluren is co-administered with drugs that are inducers of UGT1A9 (eg, phenobarbital, rifampin), or inhibitors of BCRP (eg, cyclosporine, eltrombopag, gefitinib), as these drugs may affect ataluren plasma concentrations.

In vitro data indicate that ataluren is an inhibitor of UGT1A9, organic anion transporter 1 (OAT1), organic anion transporter 3 (OAT3), and organic anion transporting polypeptide 1B3 (OATP1B3). Caution should be exercised when ataluren is co-administered with drugs that are substrates of UGT1A9 (eg, propofol, mycophenolate mofetil), OAT1, OAT3, or OATP1B3 (eg, oseltamivir, acyclovir, ciprofloxacin, captopril, furosemide, bumetanide, valsartan, pravastatin, rosuvastatin, atorvastatin, pitavastatin) because of the risk of increased concentrations of these drugs.

Based on in vitro studies, ataluren is not expected to be an inhibitor or a substrate of p-gp mediated transport.

Pharmacokinetic data indicate that no ataluren dose adjustment is required when ataluren is co-administered with systemic corticosteroids (deflazacort, prednisone, or prednisolone), and no corticosteroid dose adjustments are required when they are co-administered with ataluren. Co-administration of systemic corticosteroids with ataluren may cause more frequent instances of hypertension than does systemic corticosteroid use alone (without ataluren). However, the blood pressure data available to date are not unequivocal about any contributory role of ataluren in development of hypertension in patients who are taking corticosteriods.

6.4.6. Other Concomitant Medications

To the extent possible, administration of any prescription or over-the-counter drug products other than study medication should be minimized during the study period. Subjects should be discouraged from use of "health supplements" (eg, creatine, glutamine, coenzyme Q), herbal remedies, self-prescribed drugs, street drugs, tobacco products, or alcohol at any time during clinical studies of ataluren.

If considered necessary for the subject's well-being, drugs for concomitant medical conditions or for symptom management may be given at the discretion of the investigator. The decision to authorize the use of any drug other than ataluren should take into account subject safety, the medical need, the potential for drug interactions, the possibility for masking symptoms of a more relevant underlying event, and whether use of a concomitant medication will compromise the outcome or integrity of the study.

Subjects should be instructed about the importance of the need to inform the clinic staff of the use of any drugs or remedies (whether prescribed, over-the-counter, or illicit) before and during the course of the study. Information regarding any concomitant drugs taken by a subject during the course of the study and the reason for use will be recorded in the source documents and in the concomitant medication CRF.

6.5. Physical and Respiratory Therapy

There are neither restrictions nor prescriptions for physical or respiratory therapy during the study. Investigator sites should use local best practices in providing physical therapy support for patients participating in the study. Respiratory care guidelines as suggested by the American Thoracic Society should be followed [ATS 2004].

6.6. Dietary Restrictions

There are no specific dietary restrictions in the study.

7. SCHEDULE OF EVENTS AND STUDY PARAMETERS

7.1. Schedule of Events

The proposed types and timing of data to be recorded are described in Table 4 below. Please see Section 7.2 for cross-referenced explanations of the study procedures described in the tables.

Table 4. Schedule of Events

		Baseline	Ataluren Treatment					
Period	Screening*	a a	Audich Heddich					Post-Treatment
Study Week (±7 days)	-4 to -1	Week 1	Every 60 Weeks	Every 12 Weeks	Every 24 Weeks	Every 48 Weeks	End of Tx Week 240	6 Week Post D/C
Informed Consent {7.2.2}	x							
Clinical/medication history (7.2.3)	x							
Hepatitis screen {7.2.4}	x							
Vital signs {7.2.5}	x	x		x			x	X
Brooke UE Functional Rating Scale {7.2.6}	x							
Height/Ulna length/Arm Span {7.2.7}	x				x		x	
Physical examination (7.2.8)	x					x	x	
Weight {7.2.9}	x	x		x			x	×
Hematology {7.2.10}	x	x		x			x	x
Biochemistry {7.2.11}	x	x		x			x	x
ACTH and cortisol {7.2.12}	x	x		x			x	x
Renin and aldosterone {7.2.12}	x				As Indicated	I		
Urinalysis (7.2.13)	X	X		X			X	X
12-lead ECG {7.2.14}	x				As Indicated	l		
Echocardiogram {7.2.15}	x		X			X		χ ^b
6-minute walk test {7.2.16}	x				x		x	
Timed Function Tests {7.2.17}	x					X	x	
North Star Ambulatory Assessment {7.2.18}	x					X	x	
Egen Klassifikation Scale {7.2.19}	x					X	x	
Spirometry (7.2.20)	X				X		X	
Disease status survey {7.2.21}	x	X		x			X	
Drug administration {7.2.22}		x		x				
Drug compliance {7.2.23}				x			X	
Adverse events {7.2.24}		x		x			X	X
Concomitant medications {7.2.25}	x	x		x			X	X

Ataluren may be initiated as soon as the investigator confirms patient eligibility. Baseline procedures (excluding drug administration) do not need to be performed if Screening procedures have been performed within 7 days of anticipated initiation of ataluren treatment.

Abbreviations: ACTH = adrenocorticotropic hormone, D/C = discontinuation, ECG = electrocardiogram, Tx = treatment, UE = upper

b Only applies to patients who discontinue the study after 240 weeks of treatment.

extremity

7.2. Explanation of Study Procedures

7.2.1. Pretreatment, Treatment, and Follow-Up Periods

7.2.1.1. Screening/Baseline Period

No study-related procedures should be performed prior to the signature of the informed consent/assent document(s). Thereafter, study candidates should undergo the initial set of screening procedures as noted in Table 4. If a subject has successfully completed the necessary screening assessments and has been confirmed to be eligible by the investigator, the baseline visit for the subject can be conducted and ataluren treatment may be initiated. Ataluren may be initiated as soon as the investigator confirms patient eligibility. Baseline procedures do not need to be performed if screening procedures have been performed within 7 days of anticipated initiation of ataluren treatment. The subject will remain at the clinic until after study drug for the next 12 weeks has been dispensed and the subject/caregiver has been instructed regarding study drug storage, compliance, and administration.

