3.3. Clinical Endpoints

Primary

• Safety profile characterized by type, frequency, severity, timing, and relationship to ataluren of any adverse events or laboratory abnormalities

Secondary

• In ambulatory patients, change from baseline in 6MWD as measured by the 6-minute walk test (6MWT)

- In ambulatory patients, change from baseline in physical function as measured by the North Star Ambulatory Assessment (NSAA)
- In ambulatory patients, change from baseline in timed function tests (time to stand from supine and time to run/walk 10 meters)
- In nonambulatory patients, change from baseline in pulmonary function as measured by spirometry
- In nonambulatory patients, change from baseline in patient and parent/caregiver-reported activities of daily living, as measured by the Egen Klassifikation (EK) scale
- In all patients, changes in patient and/or parent/caregiver reports of disease status as measured by a standardized survey administered by site personnel

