7.2.21. Disease Status Survey

For all patients, a disease status survey will be administered at Screening (Visit 1) to collect retrospective information on patient and/or parent-reported changes in disease status during and after their participation in the prior PTC Therapeutics Studies 007 and 007e.

A separate survey will be administered at Week 1 (Visit 2), Week 12 (Visit 3), Week 24 (Visit 4), Week 36 (Visit 5), Week 48 (Visit 6), Week 60 (Visit 7), Week 72 (Visit 8), Week 84 (Visit 9), Week 96 (Visit 10), Week 108 (Visit 11), Week 120 (Visit 12), Week 132 (Visit 13), Week 144 (Visit 14), Week 156 (Visit 15), Week 168 (Visit 16), Week 180 (Visit 17), Week 192 (Visit 18), Week 204 (Visit 19), Week 216 (Visit 20), Week 228 (Visit 21), Week 240 (Visit 22 End-of-Treatment/Premature Discontinuation) to collect prospective information on patient and/or parent-reported changes in disease status.

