13.2.6.6 Disease Status Surveys

Information on patient and/or parent-reported changes in disease status (eg. disease symptoms and activities of daily living) during and after their participation in the prior PTC Therapeutics Studies 007 and 007e will be collected retrospectively through the use of a standardized survey administered by site personnel.

A separate survey will be administered by site personnel during the study to collect prospective information on patient and/or parent-reported changes in disease status.

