5.8.6 Disease Status Survey

For change in disease status of prospective survey data, number (%) of subjects with changes from baseline to each visit will be summarized by each category for overall subjects and a subgroup of subjects with corticosteroid use (Yes/No). If there are multiple symptoms under a category, the highest score/worse case of all available symptoms was selected for the category in the summary.

Data from the retrospective survey in studies 007 and 007e will be summarized separately.

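### The 7-day waiver of baseline procedures, as written, also lets sites skip the first prospective disease status survey, for which Screening offers no substitute baseline

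*Protocol*

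**What the plan says.** **The waiver.** Protocol 7.2.1.1 states: "Baseline procedures do not need to be performed if screening procedures have been performed within 7 days of anticipated initiation of ataluren treatment". That sentence names no exception. The footnote to Table 4 (Protocol 7.1) names one: "Baseline procedures (excluding drug administration) do not need to be performed if Screening procedures have been performed within 7 days of anticipated initiation of ataluren". SAP Table 1 carries the same footnote.

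**The surveys.** Protocol 7.2.21 describes two. The first goes to every boy: "a disease status survey will be administered at Screening (Visit 1) to collect retrospective information on patient and/or parent-reported changes in disease status", covering the time during and after Studies 007 and 007e. The prospective survey is another instrument with its own schedule: "A separate survey will be administered at Week 1 (Visit 2), Week 12 (Visit 3), Week 24", and so on every 12 weeks to Week 240. Protocol 13.2.6.6 confirms the split: "A separate survey will be administered by site personnel during the study to collect prospective information on patient and/or parent-reported changes in disease status". Table 4 and SAP Table 1 show both surveys in one row, marked at Screening and at Week 1.

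**The endpoint and its analysis.** Protocol 3.3 lists as secondary: "In all patients, changes in patient and/or parent/caregiver reports of disease status as measured by a standardized survey administered by site personnel". Protocol 10.4.6.6 asks for a descriptive summary of change from baseline in the prospective survey. SAP 5.8.6 says of the prospective data that the "number (%) of subjects with changes from baseline to each visit will be summarized by each category", and it summarizes the retrospective survey separately. SAP 6.2 defines baseline as the last valid value up to and including the day of first dose.

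**The concern.** A waiver of this kind does no harm where Screening yields the same measurement a few days earlier. That holds for vital signs, weight, hematology, biochemistry, ACTH and cortisol, urinalysis and concomitant medications, which are marked in both columns of Table 4. Adverse events are marked only at Week 1, but they need no baseline value, and Protocol 8.8 starts their reporting on the first-dose day.

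The survey is the one waivable change-from-baseline measure whose Screening and Week 1 instruments differ. The shared table row hides this, so a site that follows the schedule could reasonably believe the survey had been done at Screening. A pre-dose report of status cannot be collected after dosing starts. At stake is the completeness of the only listed secondary endpoint that covers ambulatory and nonambulatory boys together.

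**Working it through.** The plan states no figure on this point, so there is none to reproduce. The check has two parts: tracing one boy through the rules, and showing how the loss scales with the share affected.

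**1. Scheduled prospective surveys (Protocol 7.2.21).** Week 1, plus Weeks 12 to 240 in steps of 12. The second part is 240/12 = 20, so the total is 1 + 20 = 21. With the waiver used, 20 remain and the first is at Week 12.

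**2. Where the Week 12 survey falls (SAP 6.1).** Study day = assessment date − first dose date + 1. Week 12 is day 12 × 7 + 1 = 85. With the ±7-day visit window of Table 4 it lies between day 78 and day 92. The SAP windows are baseline at day 1 or earlier and Week 12 at day 42 to 126. The survey therefore maps to Week 12, after first dose, and cannot serve as baseline under SAP 6.2.

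**3. What such a boy has.** He has no prospective survey at day 1 or earlier. His only survey record in the baseline window is the retrospective one, which SAP 5.8.6 keeps apart. If change is derived by comparing a visit with baseline, it cannot be derived at any of the 20 later visits. Neither document gives a fallback rule.

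**4. Size.** The documents do not say how many boys start within 7 days of Screening or how many sites use the waiver. The possible range is 0 to about 96, the planned maximum (Protocol 1.2). For an assumed share *p*:

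- boys without a baseline = *p* × 96
- standard error relative to complete data = 1/√(1 − *p*)

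| Assumed share | Boys without baseline | Standard error ratio | Increase |
|---|---|---|---|
| 10% | 0.10 × 96 = 9.6, about 10 | 1/√0.90 = 1.054 | about 5% |
| 30% | 0.30 × 96 = 28.8, about 29 | 1/√0.70 = 1.195 | about 20% |
| 50% | 0.50 × 96 = 48 | 1/√0.50 = 1.414 | about 41% |

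The counts assume that all 96 boys enroll. The ratio does not depend on 96, but it assumes that boys with and without a baseline have the same underlying variability and are equally likely to remain under observation. It measures lost precision only and says nothing about bias.

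**5. With the survey excepted from the waiver.** All 21 surveys stand. Provided the first is completed on day 1 or earlier, it falls in the baseline window.

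**The case against.** The strongest reply is that the waiver need not reach the survey. It is permissive, and its evident purpose is to avoid repeating an assessment made days before. The prospective survey was not given at Screening, and Protocol 7.2.21, to which Table 4 refers the reader, schedules it at Week 1 without condition. A careful site could conclude that it must still be done. This stands as a reason to expect that the loss is not universal. It does not close the gap: the text does not limit the waiver to repeated procedures, and the footnote makes an exception for drug administration but not for the survey.

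Second, the survey form is not in the documents. The survey is described as collecting reported changes, so its items may themselves ask about change since the start of the study. In that case a later answer already is the change, and less or nothing would be lost. This also stands, although both analysis sections are written in terms of change from baseline.

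Third, a reader might infer that the plan would take the retrospective survey as baseline for these boys. The documents do not support that: SAP 5.8.6 confines the change summary to prospective data and reports the retrospective survey separately. What remains is a programming risk, because the SAP 6.1 baseline window accepts any record at day 1 or earlier.

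Fourth, a start within 7 days may be uncommon. Table 4 places Screening at Weeks −4 to −1, and eligibility rests on central laboratory values, with out-of-range results to be confirmed (Protocol 4.2). This is a fair reason not to favor any one row of the table above.

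Fifth, SAP 5.2 records the sponsor's decision to discontinue the study. A change to the waiver cannot recover baselines for boys already dosed. That is correct, and the fix has a separate part for them.

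**Conclusion.** The gap is real on the text. Where a site uses the waiver as written, the boy has no prospective disease status survey on or before first dose, and change from baseline for this secondary endpoint cannot be computed under SAP 6.2. The conclusion rests on two assumptions: that the site applies the waiver to the survey, and that the items record status and do not rate change.

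The extent is unknown. The 10%, 30% and 50% shares are illustrations, not estimates. A reader might infer that every boy who starts quickly is lost from every survey summary, or that a particular fraction of the cohort is missing. The documents support neither: the waiver is optional, and they give no count. His surveys from Week 12 onward can still be listed and summarized by visit.

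The consequence is limited to one descriptive secondary endpoint in a single-arm, open-label study. The primary safety endpoint is unaffected, and the survey is not among the endpoints that SAP 8.1 lists for the comparison with the natural history registry. The point is still worth acting on, because following the plan as written can lose data that cannot be recovered and prevention costs very little. Cheap improvement.

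**What to change.** - **For any boy not yet dosed.** Except the prospective disease status survey from the waiver in Protocol 7.2.1.1, Table 4 footnote a and SAP Table 1, as the footnotes already do for drug administration, and require it on or before the first-dose day. Splitting the survey row of Table 4 into retrospective and prospective rows would make the difference visible.
- **For boys already dosed without it.** State in SAP 5.8.6 that they are counted as having no baseline, report their number, and rule out the retrospective Screening survey as their baseline.

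**Cost.** The first part adds one short questionnaire at a visit the boy already attends, since Protocol 7.2.1.1 keeps him at the clinic until drug has been dispensed and instructions given. The second part is a few sentences and one count in the output. Neither touches dosing or clinical management.
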